9.9.6 Clinical Laboratory Assessments

Serum chemistry, hematology, and urinalysis laboratory tests will be performed at Screening (Switch subjects only), Baseline (Switch subjects only), Week 8, Week 28, Week 41, Week 54, and every 26 weeks thereafter. For Rollover subjects, the screening assessment will be prior data from study SD-809-C-15. Laboratory parameters that will be assessed include the following:

Table 4: Clinical Laboratory Tests

| Serum Chemistry | | |
|--|---|---|
| 
 • Sodium • Potassium • Chloride • Bicarbonate • Magnesium • Glucose • Blood urea nitrogen (BUN) | 
 • Creatinine • Total calcium • Phosphate • Uric Acid • Cholesterol • Triglycerides • Total Protein | 
 • Albumin • Total bilirubin • Direct bilirubin • Alkaline phosphatase (ALP) • Alanine aminotransferase (ALT) • Aspartate transaminase (AST) • Lactate dehydrogenase (LDH) |
| Hematology | Urinalysis | |
| 
 • Hemoglobin • Hematocrit • Red blood cell count (RBC) • Mean cell volume (MCV) • Platelets • White cell count • Neutrophils • Lymphocytes • Monocytes • Eosinophils • Basophils | 
 • Leucocytes • Nitrites • Urobilinogen • Protein • pH • Blood • Specific gravity • Ketone • Bilirubin • Glucose • Microscopic exam (if indicated) | |
| Screening Labs | | Other |
| 
 • Urine and serum pregnancy tests (women of childbearing potential only) • Follicle Stimulating Hormone (FSH) for post-menopausal women only. • Hepatitis B surface antigen (HBsAg) | | 
 • CYP2D6 genotype (blinded) • CAG repeat • Prothrombin Time |

Serum chemistry and hematology results and changes from screening/baseline will be summarized at each visit using descriptive statistics. In addition, all serum chemistry and hematology results will be categorized into the following categories using the laboratory reference ranges: below lower limit of normal, normal, above upper limit of normal. Shift tables summarizing changes in status from screening/baseline to each post-baseline visit will be presented. All laboratory results including urinalysis results will be listed.

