 - Escitalopram (Lexapro or Cipralex)¹ is allowed when administered according to approved labeling.
 - Citalopram (Celexa)² is allowed when administered according to approved labeling.
 - See [Appendix 16](#) for Celexa and Lexapro (Cipralex) dosing information
 - See Appendix 12 for a complete list of prohibited or restricted QT prolonging drugs.
11. Subject has a QTcF value >450 ms (males) or >460 ms (females), or >480 ms (with right bundle branch block) on 12-lead ECG at Screening.
- Note: Subjects with left bundle branch block are not eligible.
12. Subject has evidence of hepatic impairment at Screening, as indicated by:
- AST or ALT >2.5 times the upper limit of normal.
 - Alkaline phosphatase (ALP) or total bilirubin (TBil) >2 times the upper limit of normal (ULN)
 - Note: Subjects with Gilbert's Syndrome are eligible to participate if approved by the Clinical Monitor.
 - Note: Subjects with abnormalities in two or more of these analytes (AST, ALT, ALP, TBil) must be approved by the Clinical Monitor in order to be enrolled.
 - Prothrombin time > 4 sec prolonged.
 - Positive Hepatitis B surface antigen (HBsAg).
13. Subject has evidence of significant renal impairment at Screening, indicated by a creatinine clearance <50 mL/min, as estimated by the Cockcroft-Gault formula.
14. Subject has known allergy to any of the components of study medication.
15. Subject has participated in an investigational drug or device trial other than SD-809-C-15 within 30 days (or 5 drug half-lives) of Screening, whichever is longer.

¹ Escitalopram (Lexapro or Cipralex): The maximum allowed dose is 20 mg/day. The maximum dose for subjects ≥ 65 years old is 10 mg/day.

² Citalopram (Celexa) is allowed with the following restrictions (See Appendix 16):

- d) If the subject is a known CYP2C19 poor metabolizer, Celexa is not allowed.
- e) If the subject is > 60 years old or is receiving cimetidine, omeprazole, esomeprazole, fluconazole, fluoxetine or ticlopidine, the maximum allowed dose is 20 mg/day.
- f) If the subject is ≤ 60 years old and is not receiving any of the medications in (b) above, the maximum allowed dose is 40 mg.

16. Subject is pregnant or breast-feeding at Screening or Baseline.
17. Subject acknowledges present use of illicit drugs at Screening or Baseline.

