7.2 Safety Endpoints

Safety and tolerability will be assessed throughout the study by monitoring the following:

- Incidence of adverse events (AEs), serious AEs (SAEs), severe AEs, drug-related AEs, and AEs leading to withdrawal during the following periods:
 - The entire post-baseline period
 - During the Titration Period (from Day 1 to the end of Week 8) in Rollover subjects
 - During the Dose-Adjustment Period (from Day 1 to the end of Week 4) in Switch subjects
 - During the Extended Dose-Adjustment Period (from Day 1 to the end of Week 8) in Switch subjects who undergo dose adjustment between Weeks 4 and 8 (if at least 10% of Switch subjects have had a dose adjustment between Week 4 and Week 8)
 - During the Stable-Dose Period (Week 8 to end of study)
- Observed values and changes from baseline in clinical laboratory parameters (hematology, chemistry, and urinalysis)
- Observed values and changes from baseline in vital signs
- Observed values in ECG parameters and abnormal findings

- Numbers of subjects with QTcF values > 450 msec, > 480 msec, > 500 msec
- Counts and percentages for Columbia Suicide Severity Rating Scale (C-SSRS)
- Observed values and changes from baseline in the following:
 - Unified Huntington Disease Rating Scale (UHDRS)
 - Unified Parkinson's Disease Rating Scale (UPDRS) (dysarthria)
 - Barnes Akathisia Rating Scale (BARS)
 - Hospital Anxiety and Depression Scale (HADS)
 - Epworth Sleepiness Scale (ESS)
 - Montreal Cognitive Assessment (MoCA[®])
 - Swallowing Disturbance Questionnaire (SDQ)
- Duration of time to achieve a stable dose of SD-809, defined as the number of days from Day 1 until the first day at which the subject was taking the dose level they were receiving at Week 8.

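### Laboratory shift tables do not grade liver elevations above the normal limit, no planned output counts marked or concurrent ones, and the urinalysis endpoint is only listed

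*SAP*

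**What the plan says.** **Shift tables.** SAP 9.9.6 sorts chemistry and hematology results by the laboratory reference range into "below lower limit of normal, normal, above upper limit of normal". It then states: "Shift tables summarizing changes in status from screening/baseline to each post-baseline visit will be presented". The same section gives by-visit descriptive statistics for results and changes. SAP 8.7 defines these to include the minimum and maximum, and by default they are reported separately for the Rollover and Switch cohorts.

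**Entry limits.** Protocol 4.3, exclusion criterion 12, treats as hepatic impairment at Screening "AST or ALT >2.5 times the upper limit of normal" and "Alkaline phosphatase (ALP) or total bilirubin (TBil) >2 times the upper limit of normal (ULN"). Two notes widen entry: "Subjects with Gilbert's Syndrome are eligible to participate if approved by the Clinical Monitor", and a subject in whom two or more of the four liver tests are abnormal may enter with the same approval.

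**Record selection.** SAP 8.9 lets a scheduled record take precedence in by-visit analyses. An unscheduled result is used only when its window holds no scheduled data.

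**Urinalysis.** SAP 7.2 lists as an endpoint "Observed values and changes from baseline in clinical laboratory parameters (hematology, chemistry, and urinalysis"), and protocol 8.4 has the same endpoint. Protocol 8.3 promises shift tables for clinical laboratory results and does not except urinalysis. SAP 9.9.6 summarises and shifts only chemistry and hematology. For urinalysis it says: "All laboratory results including urinalysis results will be listed". SAP 8.10 declares two departures from the protocol (the compliance range, and the move of two motor scores to efficacy). Urinalysis is not among them.

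**The concern.** A shift table tells a reader how many subjects got worse. Here the top cell is open-ended, and the entry rules allow subjects to begin in it. A subject who enters with a mildly raised liver test and then has a marked rise is tabulated as unchanged. A subject who enters normal does register a shift, but a trivial rise and a severe one look the same.

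Safety is the purpose of this study. How many subjects had a marked liver elevation, and in how many aminotransferases and bilirubin rose together, are ordinary questions for its report. The SAP already answers the parallel question for the ECG: section 9.9.5 counts subjects with QTcF above 450, 480 and 500 msec. Nothing similar is planned for liver tests. On urinalysis, the two documents promise an analysis that the SAP's own methods section does not deliver.

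**Working it through.** The documents give no sample size, power or error-rate figure on this point, so there is nothing to reproduce. The check applies the SAP's rule to value pairs that the entry limits allow.

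**1. What the shift table records.** Rule: at or below 1 × ULN is normal, otherwise above ULN. The value pairs are hypothetical. The bands in the last column are illustrative assumptions, starting at the protocol's entry limits (ALT >2.5, >5, >10; ALP and bilirubin >2, >3).

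| Analyte | Baseline → on treatment (× ULN) | SAP 9.9.6 | With bands |
|---|---|---|---|
| ALT | 2.4 → 12 | above → above | ≤2.5 → >10 |
| ALT | 1.2 → 8 | above → above | ≤2.5 → >5 |
| Bilirubin | 1.9 → 4 | above → above | ≤2 → >3 |
| ALP | 1.9 → 5 | above → above | ≤2 → >3 |
| ALT | 0.8 → 1.1 | normal → above | ≤2.5, not counted |
| ALT | 0.8 → 12 | normal → above | ≤2.5 → >10 |

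The first four rows are no shift under the SAP. The last two share one cell.

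**2. What the mean change shows.** One subject's rise divided by cohort size, using the approximate cohort sizes in the protocol synopsis. For ALT 1.5 to 8 × ULN the rise is 8 − 1.5 = 6.5.
- Switch: 6.5/36 = 0.18 × ULN
- Rollover: 6.5/80 = 0.08 × ULN

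The same table's maximum would be at least 8 × ULN for the value and at least 6.5 × ULN for the change, provided the record is the one selected for that visit.

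**3. How many subjects could start above ULN.** The documents do not say. Assume a proportion p. The expected number is n × p, and the chance of at least one is 1 − (1 − p)^n.

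| Assumed p | Expected of 116 | Chance of ≥1 in 116 | Expected of 36 Switch | Chance of ≥1 in 36 |
|---|---|---|---|---|
| 5% | 5.8 | 0.997 | 1.8 | 0.84 |
| 10% | 11.6 | about 1 | 3.6 | 0.98 |
| 20% | 23.2 | about 1 | 7.2 | about 1 |

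Across this range, it is likely that some subjects occupy the cell in which a rise cannot register.

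**4. Unscheduled peaks.** Protocol 6.5 allows laboratory tests at unscheduled visits at the investigator's discretion. Under SAP 8.9 the Week 28 window is days 151 to 241. An unscheduled peak anywhere in it is displaced by the scheduled Week 28 record, and so is missing from that visit's shift table and its maximum. It would enter only if the window held no scheduled record. No worst-value summary is planned that would recover it.

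**5. Urinalysis.** Side by side, SAP 7.2 and protocol 8.4 promise observed values and changes, protocol 8.3 promises shift tables, SAP 9.9.6 provides a listing, and SAP 8.10 is silent.

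**The case against.** The strongest reply is that the rise remains visible. By-visit tables carry the maximum of both values and changes, by cohort, and samples are analysed centrally. Every result is listed. Under protocol 7.1.1 an abnormal test is an adverse event if it accompanies signs or symptoms or leads to a diagnosis, a therapeutic intervention or a change of study drug. SAP 9.9.1 tabulates such events by preferred term and gives exposure-adjusted rates. Protocol 9.4.2 has the Clinical Monitor review aggregate laboratory data and alert values monthly. The documents report no hepatic signal, and they nowhere promise counts by multiple of ULN. Protocol 8.3 also qualifies some laboratory summaries with the words as appropriate.

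Much of this stands. A reader might infer that the planned tables cannot show a liver signal, or that the mean change is the only other laboratory summary. The documents do not support either inference, because the minimum, maximum, listings and adverse event tables are all planned. Nor does extensive hepatic metabolism, which the protocol describes, amount to evidence of liver toxicity.

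The reply does not close the gap. A maximum is one value. It gives no number of subjects, no baseline status, and no indication of whether ALT and bilirubin rose in the same person, and by step 4 it may omit the peak. Monthly review protects subjects during the study but is not a reported analysis. Adverse event reporting depends on consequences, not on the size of the elevation. For urinalysis, a listing does not deliver changes from baseline.

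**Conclusion.** The point holds in two parts.

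First, the shift tables cannot separate a mild liver elevation from a severe one, and they record a marked rise as no shift when the subject starts above ULN. No planned output counts subjects with marked or concurrent liver elevations. The loss is one of counting and grading; the underlying data are collected and listed. No hypothesis test is affected, because none is planned. How many subjects this touches is unknown. The 5% to 20% range and the value pairs above are assumptions, and the masking of severity from a normal baseline does not depend on them.

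Second, the SAP reduces the urinalysis endpoint to a listing without declaring it. This is a plain inconsistency between sections and the smaller of the two parts. It rests on no assumption.

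Both should be corrected, since safety is what the study exists to describe and the correction is cheap.

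**What to change.** **Liver tests, SAP 9.9.6.** Add, by cohort and against baseline status, the number and percentage of subjects whose worst on-treatment value exceeds prespecified multiples of ULN. Take the worst value from all records, scheduled or unscheduled. Start at the protocol's own limits (AST or ALT >2.5 × ULN, ALP >2 × ULN, total bilirubin >2 × ULN) and add higher bands, because a single cut-point would again place 2.6 and 10 × ULN together. The bands used in the working are illustrations; the sponsor should set its own before the tables are run. Add the number of subjects with concurrent AST or ALT and bilirubin elevation, and define concurrent (for example, same sample date). The existing three-category shift tables can stay.

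**Urinalysis.** Add a categorical or shift summary to 9.9.6 so that the endpoint in SAP 7.2 is delivered. If the sponsor keeps listing only, SAP 8.10 should record that as a change from protocol 8.3 and 8.4, and SAP 7.2 should be aligned.

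**Cost.** A few paragraphs of SAP text and a few extra tables, all from data already collected. No change to visits, sampling or conduct.

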9.9.7 Other Safety Assessments

Other safety outcomes include the following:

- HADS (HADS Anxiety subscale [HADS-A] score and HADS Depression subscale [HADS-D] score)
- C-SSRS

-
- MoCA[®] (total score)

 - UHDRS
 - Parkinsonism subscore
 - Verbal fluency test score,
 - Symbol digit modalities test score
 - Stroop interference test scores of the cognitive exam, including raw color naming score, raw word reading score, raw interference score, as well as the adjusted interference score¹. The adjusted interference score can be calculated by subtracting a “predicted score”, calculated as (raw color naming *raw word reading)/(raw color naming + raw word reading), from the raw interference score.
 - Behavioral assessment item scores (the product of frequency and severity) (depressed mood, apathy, low self-esteem/guilt, suicidal thoughts, anxiety, irritable behavior, disruptive or aggressive behavior, perseverative/obsessional thinking, compulsive behavior, delusions, hallucinations), behavioral assessment total score (sum of frequency × severity item scores)
 - Functional assessment score
 - Independence scale score
 - Total functional capacity (TFC) score
 - Question 78 and 79 scores of the clinical summary section (Part VII)]

 - UPDRS dysarthria (speech score)

 - SDQ (total score)

 - BARS (summary score and global clinical assessment of akathisia score)

 - ESS (total score)

 - Duration of time to achieve a stable dose of SD-809

For all quantitative data (which includes all of these assessments except for the C-SSRS and the Question 78 and 79 scores of the UHDRS), except the duration of time to achieve a stable dose of SD-809, descriptive statistics will be presented by visit for the actual data and for the changes from baseline. For the ESS total score, SDQ, UPDRS (speech) and the BARS scores, 95% confidence intervals will be presented for the true mean changes from baseline. Descriptive statistics (and 95% confidence intervals for the true mean changes from Week 8 for the ESS total

score, SDQ, UPDRS (speech) and the BARS scores) will also be presented by visit for the actual data and for the changes from Week 8 for the UHDRS parkinsonism subscore, the UHDRS cognitive exam scores, the behavioral assessment item scores and total score, the SDQ total score, the UPDRS dysarthria speech score, the HADS scores, the BARS scores, the ESS total score, and the MoCA[®] total score. Analyses of the UHDRS cognitive exam scores will be repeated excluding sites with conflict of interest or good clinical practice violations. Results of Questions 78 and 79 from the Clinical Summary section (Part VII) of the UHDRS will be summarized by visit using counts and percentages.

For C-SSRS, the number and percentage of subjects with suicidal ideation at any post-baseline time point (overall and by individual question), suicidal behavior at any post-baseline time point (overall and by individual question), suicidal ideation or behavior at any post-baseline time point (overall and by individual question), and self-injurious behavior without suicidal intent at any post-baseline time point will be presented for each treatment group. The number and percentage of subjects with suicidal ideation [affirmative ("YES") answer to questions 1 or 2 at any post-baseline time point], with suicidal behavior [affirmative ("YES") answer to questions 6, 7, 8 or 9 at any post-baseline time points], and who completed suicide [affirmative ("YES") answer to question 10 at any post-baseline time point] post-baseline will also be presented.

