Rollover subjects will have an additional telephone contact at Week 5 with the same activities.

Switch subjects will have additional telephone contacts one week prior to their Baseline visit and at Week 7 to remind them to complete the diary card and to take or hold the morning dose on the day of their Baseline and Week 8 visits as per their assigned cohort (Rich or Sparse) dosing requirements. In addition, subjects will be reminded to return diary cards at the Baseline and Week 8 visits.

6.3.2 Clinic Visits (Weeks 4, 8, 15, 28 and every 13 weeks thereafter [all ± 3 days])

See the Schedule of Events A and B for a detailed summary of activities.

Long term treatment period clinic visits includes the following activities:

- Assessment of adverse events, chorea control (in consultation with the subject and caregiver) and concomitant medication use
- Brief physical examination (Week 28)
- Weight
- Vital signs (at Week 8, include orthostatic blood pressure and pulse)
- At Week 4, provide **Switch** subjects with a diary card to record the start time of their last meal and the time of their last dose prior to the Week 8 visit and ask them to bring the diary with them to the next clinic visit.
- Collect and review diary card (Week 8 **Switch** subjects only)
- For subjects on allowed doses of citalopram (Celexa) or escitalopram (Lexapro, Cipralext): Perform a 12-lead ECG if the dose of study drug has been increased since the last ECG was collected (Week 4)
- 12-lead ECG (Week 8)
- Clinical laboratory tests: serum chemistry, hematology, and urinalysis (Weeks 8 and 28, and every 26 weeks after Week 28)
- Urine pregnancy test (women of child-bearing potential only)(Week 28 and every 26 weeks thereafter)

- Blood sampling for PK (Week 8, **Switch** subjects only) for SD-809 ER
- Administer SD-809 post PK sample (Switch subjects scheduled for morning visits only)
- Hospital Anxiety and Depression Scale (HADS)
- Columbia Suicide Severity Rating Scale (C-SSRS): Since Last Visit version
- Montreal Cognitive Assessment (MoCA[®])
- Unified Huntington's Disease Rating Scale (UHDRS)
 - Motor
 - Cognitive
 - Behavior
 - Functional assessment (Week 28)
 - Independence (Week 28)
 - TFC (Week 28 and every 52 weeks thereafter)
 - Summary (Week 28)
- Unified Parkinson's Disease Rating Scale (UPDRS): dysarthria item
- Barnes Akathisia Rating Scale (BARS)
- Epworth Sleepiness Scale (ESS)
- Swallowing Disturbance Questionnaire (SDQ)

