- 9 Provide Diary Card to record meals and tetrabenazine dosing times for upcoming PK sampling day. Subjects should be reminded approx. 7 days before next scheduled visit to complete diary card. Subjects in the "**Rich**" cohort and "**Sparse**" cohort, scheduled for a morning visit, will be reminded to hold dose of tetrabenazine on the day of their Baseline visit. Subjects in the "**Sparse**" cohort, scheduled for an afternoon visit, will be reminded to take their usual dose(s) of tetrabenazine at home per their usual schedule on the day of their Baseline visit.
- 10 Provide diary card to record the start time of the subject's last meal and the time of their last dose of SD-809 ER prior to the Week 8 visit and ask the subject to bring the diary card with them to the next clinic visit. Subjects should be reminded approx. 7 days before next scheduled visit to complete diary card. Subjects in the "**Rich**" cohort and "**Sparse**" cohort, scheduled for a morning visit, will be reminded to hold dose of SD-809 ER on the day of their Week 8 visit. Subjects in the "**Sparse**" cohort, scheduled for an afternoon visit, will be reminded to take their usual dose(s) of SD-809 ER at home per their usual schedule on the day of their Week 8 visit.
- 11 Collect and review diary card
- 12 PK blood sample for tetrabenazine and metabolites
- 13 PK blood sample for SD-809 and metabolites. If subject requires a dose change at Week 8, PK sampling should be postponed until Week 15.
- 14 Administer tetrabenazine in clinic if subject scheduled for morning visit. If subject is scheduled for afternoon visit, they will take their usual dose of tetrabenazine at home.
- 15 Administer SD-809 ER in clinic if subject scheduled for morning visit. If subject is scheduled for afternoon visit, they will take their usual dose of SD-809 ER at home.
- 16 For subjects on allowed doses of citalopram or escitalopram:

- Week 1: A 12-lead ECG is required at this visit.
 - Week 4: If the dose of study drug has been increased since the last ECG, a 12-lead ECG is required at this visit.
- 17 After Week 28, perform clinic visits every 13 weeks until the End of Treatment Visit. Obtain safety labs and urine pregnancy test every 26 weeks after Week 28, and perform UHDRS-TFC every 52 weeks after Week 28.

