8.9 Analysis Visit Windows

For efficacy and safety by-visit analyses, data collected at post baseline scheduled visits will be included using their nominal visit. Data collected at early termination, end of treatment, and unscheduled visits will be assigned to a visit window as described below. All scheduled visits will be assigned a target study day; for the determination of target days, weeks will be assumed to have 7 days. Thus, Week 4 would have a target day of $4 \times 7 = 28$ days. For each visit, a visit window will be assigned so that anything from the midpoint to the prior target day to the midpoint to the following target day will be assigned to that visit window as shown in Table 3 below. The following rules concerning visit windows and selecting records for analysis will be used:

1. Scheduled visit has precedence.

2. If there are multiple records of the same scheduled visit, the record closest to the target day will be used for analysis. If two records are equidistant, then the earlier one will be used.
3. For a given visit, if there is no data from a scheduled visit, data from an unscheduled visit that occurs in the visit window will be used for analysis.

Table 3: Analysis Visit Window

| Visit | Target Day | Visit Window |
|-----------------------------|------------|--------------|
| Screening | -5 | (--, -5) |
| Screening Telephone Contact | -2 | (-4, -2) |
| Baseline | -1 | (-1, -1) |
| Week 1 | 7 | (1,10) |
| Week 2 | 14 | (11-17) |
| Week 3 | 21 | (18, 24) |
| Week 4 | 28 | (25, 31) |
| Week 5 | 35 | (32, 38) |
| Week 7 | 49 | (39, 52) |
| Week 8 | 56 | (53, 80) |
| Week 15 | 105 | (81, 150) |
| Week 28 | 196 | (151, 241) |
| Week 41 | 287 | (242, 332) |
| Week 54 | 378 | (333, 423) |
| Week 67 | 469 | (424, 514) |
| Week 80 | 560 | (515, 605) |
| Week 93 | 651 | (606, 697) |
| Week 106 | 742 | (698, 787) |
| Week 119 | 833 | (788, 879) |
| Week 132 | 924 | (880, 970) |
| Week 145 | 1015 | (971, 1060) |
| Week 158 | 1106 | (1061, 1152) |
| Week 171 | 1197 | (1153, --) |

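### After Week 28, 42 of the 44 by-visit rows for the UHDRS functional scales can hold only subjects leaving treatment in that window, not the cohort still on drug

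*SAP*

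**What the plan says.** **Rating schedule.** Among the long-term clinic visits, Protocol 6.3.2 lists "Functional assessment (Week 28", "Independence (Week 28" and "Summary (Week 28", in each case with no later week. For TFC it lists "TFC (Week 28 and every 52 weeks thereafter". Protocol 6.3.3 repeats all four at End of Treatment/ET. Schedules A and B (SAP Tables 1 and 2) agree. The column for visits every 13 weeks after Week 28 is blank for the first three scales. It is marked for TFC, with the footnote "perform UHDRS-TFC every 52 weeks after Week 28". The visits themselves are more frequent: "After Week 28, perform clinic visits every 13 weeks until the End of Treatment Visit".

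**Reporting.** SAP 9.9.7 applies one rule to its quantitative scores, including Functional Assessment, Independence and TFC: "descriptive statistics will be presented by visit for the actual data and for the changes from baseline". Clinical Summary Questions 78 and 79 (Q78/79) are excepted from that rule and summarised by visit as counts and percentages.

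**Placement of values.** SAP 8.9 states: "Data collected at early termination, end of treatment, and unscheduled visits will be assigned to a visit window as described below". SAP 8.5.2 rules out imputation of missing endpoints. SAP 8.7 bases percentages on non-missing data.

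**Baseline.** Schedule B takes these four scales for Rollover subjects from First-HD (Week 12 or earlier). Under SAP 8.7, an assessment scheduled neither at First-HD Week 13 nor at the ARC-HD Baseline visit uses the last value before First-HD Day 1.

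**The concern.** The by-visit display suits scales rated at every clinic visit. Here it meets a schedule in which most visits have no rating, and the windowing rule fills the gaps with values from subjects who are leaving treatment. A subject who stays on drug attends the visit but contributes nothing to that row. A subject whose End of Treatment or Early Termination visit falls in the window does contribute. A table row labelled with a late study week would naturally be read as function on SD-809 at that week, and it is not that.

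This matters because the first study objective includes maintenance therapy, Protocol 1.1 describes the disease as progressive, and Protocol 6.7.3 reports that the UHDRS may suit tracking of longitudinal change. No other planned summary compensates. The change-from-Week-8 list in SAP 9.9.7 leaves these scales out, and the repeat restricted to scheduled visits in SAP 9.7 is for TMC only.

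**Working it through.** **1. Reproduce SAP Table 3.** Target day = 7 × week: 7 × 80 = 560, 7 × 132 = 924, 7 × 171 = 1197. These match the table, as do the other post-baseline rows.

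**2. Rows after Week 28.** Weeks 28 + 13k for k = 1 to 11: 41, 54, 67, 80, 93, 106, 119, 132, 145, 158, 171. That is 11 rows.

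**3. Scheduled ratings in those rows.** Functional Assessment, Independence and Clinical Summary: none. TFC at 28 + 52k: Weeks 80, 132 and 184. Week 184 is day 7 × 184 = 1288. It has no row of its own and lies inside the open-ended Week 171 window, which starts at day 1153.

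| Scale | Rows after Week 28 | Rows with no scheduled rating |
|---|---|---|
| Functional Assessment | 11 | 11 |
| Independence | 11 | 11 |
| Clinical Summary (Q78/79) | 11 | 11 |
| TFC | 11 | 9 (all but Weeks 80 and 132) |
| Total | 44 | 42 (42/44 = 95%) |

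For the three scores reported as change from baseline: 11 + 11 + 9 = 31 of 33 rows (94%).

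**4. What can enter such a row.** Take Functional Assessment at Week 93, window days 606 to 697. A subject on drug at the target day, 651, has a clinic visit but no scheduled rating. A subject with an End of Treatment/ET visit on day 640 has a rating, and SAP 8.9 assigns it to Week 93. The only other source is an unscheduled visit. There these scales are at the investigator's discretion under the schedule footnote, and the list of discretionary assessments in Protocol 6.5 does not name them.

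**5. How far a row can be from the cohort (illustration only).** The documents give no stopping rate. Assume a constant rate of a = 5% to 30% per year, the planned N of about 116, and no study closure within the row. With λ = −ln(1 − a)/364, the expected number in a row is 116 × [exp(−λ·start) − exp(−λ·(end + 1))], and the number still on drug is 116 × exp(−λ·target).

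| Row (days) | a | Stopping in window | On drug at target day |
|---|---|---|---|
| Week 41 (242–332) | 5% | 1.4 | 111 |
| Week 41 (242–332) | 30% | 7.8 | 88 |
| Week 158 (1061–1152) | 5% | 1.3 | 99 |
| Week 158 (1061–1152) | 30% | 3.5 | 39 |

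Across the ten closed rows this gives about 1 to 8 subjects per row, against 39 to 111 still treated. A row in which the study closes would hold many more. These figures show the contrast and are not a prediction.

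**The case against.** The strongest reply is that these are secondary descriptive summaries in an open-label, single-arm study with no formal testing (SAP 8.1) and a sample size not statistically based (SAP 8.2). The functional scales get only a plain table without confidence intervals. Each row shows its number of observations, all data are listed, and change from baseline is within subject, so row composition distorts it less than it distorts raw means. All of that is true and limits the harm. But a small count does not tell the reader that the row consists of leavers, and the percentages for Q78/79 have only those leavers as denominator.

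Some stronger readings are tempting but not supported:

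- *The study gives no estimate of longer-term functional change.* Week 28 is a scheduled rating on all four scales, TFC is also scheduled at Weeks 80 and 132, and scheduled records take precedence under SAP 8.9.
- *Any trend across rows is just a trend in who stopped when, with dropouts early and completers late.* Treatment ends when SD-809 becomes commercially available in the U.S., so a completer's time on drug depends on enrolment date, and completers can share a row with dropouts. Nothing in the documents shows that stopping is related to function.
- *Each row will hold roughly 116/11 subjects.* That assumes an even spread and nobody stopping before day 242. The documents support neither.
- *Change is reported by visit for all four scales.* Q78/79 have no change score.
- *An annualised slope from a linear mixed model is needed.* It would assume roughly linear change. For Rollover subjects its starting point precedes First-HD dosing, so the slope would span both studies and, for prior-placebo subjects, time off drug. Q78/79 are not treated as quantitative. Without a control, the slope could not separate drug effect from disease progression.

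**Conclusion.** The point holds as a reporting defect that follows from rules stated in the plan. Applied as written, the schedule, SAP 8.9 and SAP 9.9.7 together produce 42 of 44 post-Week-28 rows that can contain only subjects leaving treatment in that window, whether early terminators or subjects at study closure. Those rows do not describe the cohort still on drug at the labelled week.

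The count rests on Table 3 and the two schedules. It has two qualifications. A discretionary unscheduled rating could add a value to any row. If a Week 184 TFC were assigned to the open Week 171 window, the count would be 41 of 44. The number of subjects per row, and the direction of any distortion, cannot be derived from the documents. The Week 28 rows and the TFC rows at Weeks 80 and 132 remain usable. The change is worth making because it is cheap and prevents a misreading; no primary conclusion depends on it.

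**What to change.** In SAP 9.9.7, for Functional Assessment, Independence, TFC and Q78/79:

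- Present by-visit rows only where the scale is scheduled: Week 28 for all four, and Weeks 80 and 132 for TFC.
- Exempt these scales from the SAP 8.9 assignment of Early Termination and End of Treatment values to visit windows.
- Add one row for the End of Treatment or last on-treatment value. Show actual value and change from baseline (counts and percentages for Q78/79) together with a summary of time on SD-809, by cohort and separately for completers and early terminators.
- State that for Rollover subjects the baseline for these scales is the value before First-HD dosing (SAP 8.7), so the change spans both studies.

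The cost is SAP wording and slightly more programming on data already collected, with no extra visits or ratings. End of Treatment values would no longer appear under a nominal week; the summary of time on drug carries that information instead.
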